4.1.3. Other Endpoints

- [REDACTED]
- [REDACTED]

4.2. OVERALL STUDY DESIGN

This study is a randomized, double-blind, parallel group, placebo-controlled, multicenter, Phase II study.

Approximately 60 eligible subjects with a centrally confirmed IPF diagnosis are planned to be randomized in a 2:1 ratio to GLPG1205 100 mg q.d. taken as 2 capsules, or matching placebo q.d. administered for 26 weeks on top of local standard of care. Standard of care is defined as receiving nintedanib, pirfenidone or neither nintedanib nor pirfenidone.

Individual dose reductions of GLPG1205 will be allowed once in case of intolerance or toxicity at the discretion of the investigator (Section 5.2). Subjects may have their dose of IMP reduced from 100 mg (2 capsules) q.d. to 50 mg (1 capsule) q.d. for the remainder of the study. Should the intolerance or toxicity continue, IMP may be discontinued, and the subject may be withdrawn from the study (refer to Section 4.3.5).

During the course of the study (post randomization) further adaptations of the treatment with nintedanib or pirfenidone due to e.g. intolerance or initiation of either nintedanib or pirfenidone is allowed based on the medical needs of the individual as judged by the investigator.

Enrolled subjects will come to the clinical study center at screening, Day 1 (baseline), Week 2, Week 4, Week 8, Week 12, Week 16, Week 20, Week 26, and, if applicable (i.e. for

early IMP discontinuation), the end of treatment visit (EOT). In addition, a follow-up visit will be planned 4 weeks after the last administration of IMP (i.e. Week 30/EoS). The end of the study is reached when the last follow-up visit as planned according the schedule of activities (Section 6.10) of the last subject is performed.

Subjects who stop IMP early need to be encouraged to complete the EOT and follow-up visit for safety assessments and pulmonary function, but will not be obliged to do so.

To enhance the safety of the subjects and integrity of the study data, an Independent Data Monitoring Committee (IDMC) will be implemented and clinical endpoint adjudication will be performed (see Section 8 for additional information).

For the in- and exclusion criteria please refer to Section 4.3.2, “[Inclusion Criteria](#)” and Section 4.3.3, “[Exclusion Criteria](#)”.

A schematic diagram of clinical study design is provided ([Figure 1](#)).

[figure not shown]

Figure 1 GLPG-1205-CL-220 Study Design

The subjects will be in the study for a duration of approximately 34 weeks: up to 4 weeks of screening, 26 weeks of treatment, and 4 weeks of follow-up.

For detailed info regarding dosage form, packaging and labeling of the IMP please refer to Section 5.2, “[Dosage and Administration](#)” and Section 5.3, “[Packaging, Labeling and Distribution](#)”.

4.3. STUDY POPULATION

4.3.1. Sample Size

Approximately 60 subjects are planned to be randomized into the study. In principle, it is aimed to achieve a balanced study population with regards to the background standard of care.

For the justification of sample size, including assumptions and power considerations please refer to Section 7.1 “[Determination of Sample Size](#)”.

4.3.2. Inclusion Criteria

Subjects who meet all of the following criteria are eligible for the study:

1. Signed informed consent form (ICF) obtained prior to any study-related procedures and/or assessments performed.
2. Males or females of non-child-bearing potential, aged ≥ 40 years on the day of signing the ICF.

Note: female subjects are considered of non-childbearing potential if they meet one of the following criteria:

- No menses for 12 or more months without an alternative medical cause AND a follicle-stimulating hormone (FSH) level >40 IU/L
 - Permanently surgically sterile (bilateral oophorectomy, i.e. surgical removal of ovaries, bilateral salpingectomy or hysterectomy, i.e. surgical removal of uterus)
3. Criterion modified per amendment.
 - 3.1 A diagnosis of IPF within 5 years prior to the screening visit as per applicable American Thoracic Society (ATS)/European Respiratory Society (ERS)/Japanese Respiratory Society (JRS)/Latin American Thoracic Association (ALAT) guideline [6, 24]. Subjects receiving local standard of care for the treatment of IPF, defined as either pirfenidone or nintedanib at a stable dose for at least 8 weeks before screening, and during screening; or neither pirfenidone nor nintedanib (for any reason). A stable dose is defined as the highest tolerated dose. Prednisone at steady dose ≤ 10 mg/day or equivalent glucocorticoid dose is allowed (stabilized 4 weeks prior to screening and continued without variation of dose or regimen). Supportive care like supplemental oxygen or pulmonary rehabilitation is allowed.
 4. Criterion modified per amendment.
 - 4.1 Chest HRCT historically performed within 12 months prior to the screening visit and according to the minimum requirements for IPF diagnosis by central review (see [Appendix 1](#)) based on subject's HRCT only (if no lung biopsy [LB] available), or based on both HRCT and LB (with application of the different criteria in either situation). If an evaluable HRCT <12 months is not available, a HRCT can be performed at screening to determine eligibility, according to the same requirements as the historical HRCT.
 5. Criterion modified per amendment.
 - 5.1 Meeting all of the following criteria at screening and during the screening period:
 - a. FVC $\geq 50\%$ predicted of normal
 - b. Disease progression, defined as a decline of FVC (% predicted or mL) at the investigator's discretion, during the 9 months prior to the screening period and confirmed at the screening visit
 - c. Diffusing capacity for the lungs for carbon monoxide (DLCO) $\geq 30\%$ predicted of normal (corrected for hemoglobin) (see Section [6.4.4](#))
 - d. Ratio of forced expiratory volume in one second (FEV₁) to FVC ≥ 0.70
 6. Criterion modified per amendment.
 - 6.1 In a stable condition and suitable for study participation based on the results of a medical history, physical examination, vital signs, 12-lead ECG, and laboratory evaluation. Stable condition is based on the clinical judgment of the investigator, co-morbidities should be treated according to the local applicable guidelines. Concomitant medication for chronic co-morbidities should be stabilized from 4 weeks before screening and during the screening period (stable defined as no clinically relevant change according to the investigator's judgement).
 7. Estimated minimum life expectancy of 12 months for non-IPF related disease in the opinion of the investigator.

8. Male subjects with female partners of child bearing potential are willing to comply with the contraceptive methods described in the protocol (see Section 4.3.4.1) prior to the first dose of the IMP, during the clinical study, and for at least 12 weeks after the last dose of the IMP.
9. Criterion modified per amendment.
 - 9.1 Able to walk at least 150 meters during the 6MWT at screening; without having a contra-indication to perform the 6MWT (see Appendix 3), or without a condition putting the subject at risk of falling during the test (at investigator's discretion). The use of a cane is allowed, the use of a stroller is not allowed at all under any circumstances.
10. Able to understand the importance of adherence, and willing to comply to study treatment, study procedures and requirements as per study protocol, including the concomitant medication restrictions.

4.3.3. Exclusion Criteria

Subjects meeting one or more of the following criteria cannot be selected for this study:

1. Known hypersensitivity to any of the IMP ingredients or a history of a significant allergic reaction to any drug as determined by the investigator (e.g. anaphylaxis requiring hospitalization).
2. Criterion modified per amendment.
 - 2.1 Current immunosuppressive condition (e.g. human immunodeficiency virus [HIV] infection, congenital, acquired, medication induced, organ transplantation).
3. Criterion modified per amendment.
 - 3.1 Positive blood testing for hepatitis B surface antigen (HBs Ag) or hepatitis C virus antibody (if positive, confirmed by hepatitis C virus (HCV) RNA positivity). *Note:* Subjects with a resolved hepatitis A at least 3 months prior to first dosing of the IMP can be included.
4. History of malignancy within the past 5 years (except for carcinoma *in situ* of the uterine cervix, basal cell carcinoma of the skin that has been treated with no evidence of recurrence, and prostate cancer medically managed through active surveillance or watchful waiting, and squamous cell carcinoma of the skin if fully resected).
5. Criterion modified per amendment.
 - 5.1 Clinically significant abnormalities detected on 12-lead ECG of either rhythm or conduction, including prolongation of QTc or known long QTc syndrome. For any interval measurements e.g. when deciding if QT interval corrected for heart rate using Fridericia's formula [QTcF] is >450 ms [male], OR >460 ms [female], when triplicate ECG are performed (baseline), a single outlier value per interval should be considered (i.e. worst case scenario). Of note, a first-degree heart block will not be considered as a significant abnormality.
6. Criterion deleted per amendment.
7. Acute IPF exacerbation within 3 months prior to screening and during the screening period (see Appendix 2).
8. Lower respiratory tract infection requiring antibiotics within 4 weeks prior to screening and/or during the screening period.

9. Interstitial lung disease associated with known primary diseases (e.g. sarcoidosis, amyloidosis), exposures (e.g. radiation, silica, asbestos, coal dust), and drugs (e.g. amiodarone).
10. History of lung volume reduction surgery or lung transplant.
11. Unstable cardiovascular, pulmonary (other than IPF) or other disease within 6 months prior to screening or during the screening period (e.g. coronary heart disease, heart failure, stroke).
12. Any other clinical condition or circumstance that in the opinion of the investigator may make him or her unsuitable for inclusion or unable to complete the study or comply with study procedures and requirements.
13. Criterion modified per amendment.
 - 13.1 Moderate to severe hepatic impairment (Child-Pugh B or C) and/or abnormal liver function test (LFT) at screening, defined as aspartate aminotransferase (AST) and/or alanine aminotransferase (ALT) and/or bilirubin 1.5x and/or gamma glutamyl transferase (GGT) 3x upper limit of normal (ULN) range. Retesting is allowed once for abnormal LFT.
14. Criterion modified per amendment.
 - 14.1 Abnormal renal function defined as estimated creatinine clearance <30 mL/min using Cockcroft-Gault equation. Retesting is allowed once.
15. Criterion modified per amendment.
 - 15.1 Underwent major surgery within 3 months prior to screening or who has major surgery planned during the study period. Note: being on a lung transplant list is allowed.
16. Hemoglobin level <10 g/dl. Retesting is allowed once.
17. Criterion modified per amendment.
 - 17.1 Subject participating in a drug, device or biologic investigational research study, concurrently with the current study, within 12 weeks or 5-half-lives of the agent, whichever is longer, prior to screening, or prior participation in an investigational drug antibody/biologic study within 6 months prior to screening.
18. Criterion modified per amendment.
 - 18.1 Use any of the following therapies within 4 weeks before screening and during screening, or planned during the study:
 - a. Warfarin
 - b. Imatinib
 - c. Endothelin receptor antagonists (e.g. ambrisentan, bosentan and macitentan)
 - d. Azathioprine
 - e. Cyclophosphamide
 - f. Cyclosporine A
 - g. Methotrexate
 - h. Sildenafil
 - i. Prednisone at steady dose >10 mg/day or equivalent
19. Criterion modified per amendment.

- 19.1 Use any of the following therapies within 5 half-lives before screening and during screening, or planned during the study
- medications which are known BCRP substrates (see [Appendix 5](#))
 - medications which are known dual CYP3A4 and CYP2C19 inhibitors (see [Appendix 8](#))
 - medications which are known to be CYP3A4 or CYP2C19 strong inducers (see [Appendix 9](#))
20. Current alcohol or substance abuse in the opinion of the investigator.

4.3.4. Prohibition and Restrictions

4.3.4.1. Precautions for Sexual Intercourse

Highly effective contraceptive measures for males must be documented in the source documents.

Non-vasectomized male subjects with female partners of childbearing potential must be willing to use a condom from the time of the first dose of IMP, during the clinical study, and for at least 12 weeks after the last dose of IMP, in addition to having their female partner use one of the following forms of contraception:

- Combined (estrogen and progesterone containing) (oral, intravaginal, transdermal) hormonal contraception associated with inhibition of ovulation
- Progesterone-only hormonal (oral, injectable, implantable) contraception associated with inhibition of ovulation
- Intrauterine device or intrauterine hormone-releasing system

Periodic abstinence (e.g., calendar, symptothermal, postovulation methods), declaration of abstinence for the duration of a clinical study, withdrawal, spermicides only and lactational amenorrhea method are not acceptable as methods of contraception.

In case where the female partner of a male subject has undergone documented surgical sterilization (bilateral oophorectomy, i.e. surgical removal of ovaries, bilateral salpingectomy or hysterectomy, i.e. surgical removal of uterus) that was performed more than 1 year before screening, then the subject is not required to use an additional form of contraception.

Vasectomized male subjects with female partners of childbearing potential are not required to use an additional form of contraception providing that surgical sterilization has been successful (documented azoospermia by semen analysis).

No sperm donation is allowed from first dose of the clinical study during the clinical study until 12 weeks after the last dose.

4.3.4.2. Prior and Concomitant Medications

Concomitant therapies taken for the long-term treatment of preexisting chronic conditions can continue during the study provided they are in accordance with the inclusion and exclusion criteria (see Section 4.3.2 and Section 4.3.3, respectively). All concomitant medicines must be locally approved and administered at a dose that is considered standard-of-care for the treated indication. It is required that these medications be stabilized prior to study entry and if

possible continued without clinically relevant changes (at the discretion of the investigator) during the study.

In a case where additional concomitant medication needs to be administered or dose adjustments for IPF and other preexisting conditions need to be performed during the study, the risk/benefit to the subject should be carefully assessed and consideration given to the timing of any necessary introduction of new medications. As such, adaptation or initiation of treatment with nintedanib or pirfenidone (both post randomization) or other non-excluded concomitant medications are allowed throughout the study based on the medical need of the individual patient.

Note: Subjects receiving either pirfenidone or nintedanib have to be on a stable dose for at least 8 weeks before screening, and during screening. A stable dose is defined as the highest tolerated dose.

All decisions on the start and stop of the intake of nintedanib or pirfenidone or the need for dose adjustments during the study will be made by the investigator and recommendations of the respective local SmPCs should be followed, as done in normal clinical practice.

In vitro assays indicated an inhibition by GLPG1205 of the drug transporters BCRP and OCT2, at a concentration being equivalent to human exposure of 100 mg GLPG1205. Preliminary in vivo data from a clinical drug-drug interaction study assessing the effect of GLPG1205 on OCT2 and BCRP probe substrates show that there is only clinically relevant inhibition of BCRP by GLPG1205 (approximately 3 fold exposure increase), therefore inclusion of subjects with stable chronic illness on stable medications which are transported by known BCRP is not allowed and known BCRP substrates are prohibited during the study. A (non-exhaustive) list of BCRP substrates is provided in [Appendix 5](#).

Inclusion of patients with stable chronic illness on stable medications which are transported by OCT2 transporters (less than 2 fold exposure increase observed) should be decided on a case-by-case basis, taking into account the medical history, concomitant medication of the patient and benefit/risk profile. The CRO's medical monitor or sponsor's medical lead can be contacted when deemed necessary by the investigator, specifically for medication with a narrow therapeutic index and/or a risk of (un)predictable AEs. This is specifically to be done for medication that is transported by OCT2 and has the risk to prolong QT interval. A (non-exhaustive) list of OCT2 substrates is provided in [Appendix 6](#).

Statins have different pathways involved in their disposition (either via metabolic enzymes and/or via transporters) and since it cannot be ruled out that GLPG1205 could interfere with some of those pathways (leading to cumulative net effect difficult to predict from in vitro studies) and to date, no in vivo clinical drug-drug interaction studies have been conducted yet, there is a need to further monitor subjects who may be on statin background therapy. Monitoring of liver function tests and creatine kinase (CK) is implemented during the study as per local guidance for statins in clinical practice.

The use of medication known to prolong QT interval during the study needs to be based on a benefit-risk evaluation by the investigator, e.g. in the case of atrial fibrillation. In other situations (e.g. the initiation of macrolides or fluoroquinolones in case of a lower respiratory tract infection), when a medication known to prolong or potentially prolonging QT is indicated, IMP can be interrupted after clinical assessment of the subject's profile, including the baseline QTcF and how this has changed over time. If the investigator elects to continue IMP, additional

monitoring will be performed as per investigator's judgment. A non-exhaustive list of medication known to prolong QT interval is provided in [Appendix 10](#).

All medications that are not allowed in accordance with the inclusion and exclusion criteria should not be used during the study.

It is highly recommended that the CRO medical monitor (as per study contact list) or sponsor's study physician (if the former is not available) are consulted before the initiation of new medications, in particular medication known to prolong QT interval, and medication known to be transported by OCT2 transporters.

All concomitant therapies, as well as their changes occurring during the study are to be recorded on the relevant case report form (CRF) page(s), along with the reason for and details of therapy use. All prior surgeries will be recorded on the relevant CRF page(s).

4.3.4.3. Food and Beverage Restrictions

The comparison of exposures to GLPG1205 achieved after oral administration of GLPG1205 as a capsule in fed or fasted state (GLPG1205-CL-102) indicates that food has no influence on exposure, therefore there is no food restriction in the current study.

4.3.4.4. Other Prohibitions and Restrictions

No blood donation is allowed during the study.

4.3.5. Removal of Subjects from Therapy or Assessments

A subject may be withdrawn from the clinical study at any time without the subject's consent if the investigator or sponsor determines that it is not in the best interest of the subject to continue participation. In such case, the reason for withdrawal will be documented in the source documents, and the subject will be asked to complete the EOT visit and follow-up visit for safety assessments and pulmonary function.

Study treatment should be discontinued by the investigator (preferably after discussion with the CRO medical monitor, for any of the following conditions:

- Life-threatening AE or a SAE that places the subject at immediate risk
- Serious infections (those requiring parenteral antimicrobial therapy and/or hospitalization)
- Arrhythmia or conduction abnormality, including but not limited to prolonged QT interval corrected for the heart rate using Fridericia's formula (QTcF), where the severity is categorized as Common Terminology Criteria for Adverse Events (CTCAE) Version 5.0 Grade 3 or higher (i.e. QTcF \geq 501 ms or an increase from baseline (Visit 2) in QTcF of $>$ 60 ms) on at least 2 separate ECGs at the same visit
- Increase in liver function tests:
 - AST and/or ALT elevations $>$ 8x ULN: IMP treatment should be withheld and the LFTs should be repeated. IMP should be discontinued if the results are confirmed
 - AST and/or ALT elevations $>$ 3x ULN and $<$ 8xULN: IMP treatment should be withheld. If LFTs do not return to normal within 2 weeks then the IMP should be discontinued. If LFTs return to normal within 2 weeks then IMP could be restarted with close monitoring (e.g. repeat testing twice per week for the first 2 weeks then

weekly for the following month). In the event LFTs become abnormal at any subsequent point during the study (i.e. after rechallenge) then the IMP should be discontinued.

- AST and/or ALT elevations $>3x$ ULN and total bilirubin level (TBL) $>2x$ ULN or international normalized ratio (INR) >1.5 : IMP treatment should be withheld and the LFTs should be repeated. IMP should be discontinued if the results are confirmed.
- AST and/or ALT elevations $>3x$ ULN with the appearance of fatigue, nausea, vomiting, right upper quadrant pain or tenderness, fever, rash and/or eosinophilia ($>5\%$): IMP treatment should be withheld, LFT repeated and IMP discontinued if LFT confirmed or if symptoms and signs persist

When test results need to be confirmed, the subject should return to the investigational site and be evaluated as soon as possible, preferably within 48 hours from awareness of the abnormal results. This evaluation should include laboratory tests, detailed history and physical assessment. In addition to repeating AST and ALT, laboratory tests should include albumin, creatine kinase, total bilirubin, direct and indirect bilirubin, gamma-glutamyl transferase (GGT), INR, and alkaline phosphatase. A detailed history, including relevant information (e.g. review of ethanol, recreational drug and supplement consumption, family history, sexual history, travel history, history of contact with a jaundiced subject, surgery, blood transfusion, history of liver or allergic disease, and work exposure) should be collected. Further testing for acute hepatitis A, B or C infection and liver imaging (e.g. biliary tract) may be warranted. All cases confirmed on repeat testing with no other cause for LFT abnormalities identified at the time should be considered potential Hy's Law cases irrespective of availability of all the results of the investigations performed to determine etiology of the abnormal LFTs. Such potential Hy's Law cases should be reported as SAEs.

The investigator may also decide to discontinue IMP (preferably after discussion with the CRO medical monitor, who may consult and must inform the sponsor's study physician) for any of the following reasons:

- Use of concurrent therapy that was not permitted
- Noncompliance with the IMP treatment
- Noncompliance with the clinical study procedures (e.g. missing more than 2 visits)
- Serious or severe AEs
- Worsening of disease condition, which in the investigator's opinion needs an alternative treatment approach not being covered in the clinical study (e.g. rescue medication)
- In case of interruption of IMP for cumulatively >30 days

Every effort should be made to keep subjects in the study and on treatment. However, the investigator can consider stopping the treatment with IMP, preferably after consultation with the sponsor's study physician, in case of concerns about the subject's safety, major protocol noncompliance, serious or severe AEs or worsening of the disease condition, which in the investigator's opinion needs an alternative treatment approach not being covered in the clinical study (e.g. rescue medication).

When IMP is discontinued, the subject will be requested to return for the EOT and EOS Visits to allow safety Follow-up.

Subjects will be informed prior to clinical study entry that they are allowed to withdraw from the clinical study. At any time and for any reason, a subject's participation in the clinical

study may terminate at his/her request without prejudice to his/her future medical care. The subject will be encouraged to share the reason(s) for withdrawal so this can be documented in the source documents, and to complete the EOT visit and follow-up visit for safety assessments and pulmonary function, but will not be obliged to do so.

Subjects who withdraw from the clinical study without contact with the site (lost to follow-up) should be contacted by the site so that their health status can be assessed and documented in the source documents. The site should make every effort to understand whether the subject is alive, including checking the medical records, contacting general practitioner or relatives, if necessary. All attempts (at least 3) must be documented in the source documents.

Subjects who drop out before the first administration of the IMP will be replaced. Subjects who stop taking IMP for any reason will not be replaced.

The sponsor has the right to terminate the clinical study at any time in case of safety concerns or if special circumstances concerning the IMP or the company itself occur, making further treatment of subjects impossible. In this event, the investigator(s) and relevant authorities will be informed of the reason for clinical study termination.

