2. SGRQ
3. Physical examination
4. AE assessment and concomitant medication
5. 12-lead ECG (triplicate)
6. Vital signs (supine SBP, DBP, heart rate, oral or tympanic body temperature, and respiratory rate)
7. Spirometry (and submit data to central reader)
8. Predose PK blood sample (for GLPG1205, and if applicable nintedanib or pirfenidone concentration analysis)
9. Safety blood sampling for clinical laboratory evaluations (hematology, coagulation and clinical chemistry)
10. Safety urine sampling for clinical laboratory evaluations (urinalysis)
11. [REDACTED]
12. [REDACTED]
13. 6MWT [REDACTED]
14. [REDACTED]
15. Repeat spirometry if acceptability and repeatability criteria as specified by ATS/ERS/JRS/ALAT are not met after confirmation by central spirometry reader
16. Randomization if all in- and exclusion criteria are met)
17. Dispense subject diary and provide instructions on IMP intake, timing and storage
18. Dispense IMP
19. Dosing IMP and if applicable nintedanib or pirfenidone on site

Visit 3, 5, 6, and Visit 7 (if applicable)

Subjects who are taking nintedanib or pirfenidone can do this at home or on site according to their normal routine.

1. SGRQ (Visit 6)
2. Physical examination (Visit 3 and 6)
3. AE assessment and concomitant medication
4. 12-lead ECG (Visit 3 and 6, single)
5. Vital signs (supine SBP, DBP, heart rate, oral or tympanic body temperature, and respiratory rate)
6. Spirometry (Visit 5, 6 and 7)
7. PK blood sample (Visit 6: predose sample for GLPG1205, and if applicable postdose sample for nintedanib or pirfenidone concentration analyses)
8. Safety blood sampling for clinical laboratory evaluations (hematology, coagulation and clinical chemistry)
9. [REDACTED]

10. [REDACTED]
11. Safety urine sampling for clinical laboratory evaluations (urinalysis)
12. Dosing IMP on site
13. Dispense subject diary and provide instructions on IMP intake, timing and storage
14. Collect subject diary
15. Dispense IMP
16. Collect returned IMP and review IMP compliance

Visit 4 and Visit 8 (if applicable)

Subjects who are taking nintedanib or pirfenidone, should bring these to the site for onsite dosing.

1. Physical examination
2. AE assessment and concomitant medication
3. 12-lead ECG (Visit 8, single)
4. Vital signs (supine SBP, DBP, heart rate, oral or tympanic body temperature, and respiratory rate)
5. Spirometry
6. Predose PK blood sample (for GLPG1205, and if applicable nintedanib or pirfenidone concentration analysis)

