6.5.3. Physical Examination

Physical examinations will be conducted by a physician, trained physician's assistant, or nurse practitioner as acceptable according to local regulation at visits specified in the schedule of activities in Section 6.10 (see also Section 6.1, "Timing of Assessments"). The person conducting the physical examination will document this in the subject's medical records. Clinically significant abnormal findings should be recorded as AEs. At screening the physical examination will include height and weight, and weight should be measured at Visit 9/EOT and Visit 10/EOS.

6.5.4. 12-lead Electrocardiogram

At the time points specified in the schedule of activities Section 6.10 (see also Section 6.1, "Timing of Assessments"), a 12-lead ECG will be recorded and results will be sent for central reading. ECG recordings will be performed before blood/urine sampling and after subjects rested for 5 minutes in supine position. In case an indwelling catheter is used, ECGs may be recorded after blood sampling, provided that there is at least 30 minutes between catheter insertion and the ECG recording. When catheter insertion would fail, the 12-lead ECG needs to be taken before the venipuncture and at least 30 minutes after the failed attempt. Triplicate ECGs will be performed at baseline (Visit 2) only within a time span of 6 minutes, with an approximate 3-minute interval between ECGs. Parameters to be recorded include the following: heart rate, PR interval, QRS interval, uncorrected QT interval, morphology and rhythm analysis (QTcF will be derived during the statistical analysis). ECG parameter normal ranges are presented in Appendix 4. QTcF will be considered as normal if ≤ 450 ms (male) and ≤ 460 ms (female), while subjects experiencing a prolongation of QTcF to ≥ 501 ms or an increase from baseline >60 ms should be discontinued from IMP (see Section 4.3.5). Immediately after recording, the ECGs will be reviewed by the investigator on clinical significant abnormalities. This immediate review during the visit needs to be documented in the subject's source. After receipt of the central report, also all flagged ECG abnormalities need to be assessed by the investigator on clinical relevance. All clinically significant abnormal ECG values should be recorded as AEs.

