5.3.3.2. Derivation Rules

Derived Parameters

The QTcF values will be used as available in the database.

Handling of ECGs Measured in Triplicate

If ECG is collected in triplicates/duplicates, the following approach will be taken.

The mean of the triplicate/duplicate ECG values will be calculated for each individual ECG parameter, without rounding the result. These calculated means will constitute the analysis values; any derivation (e.g. change from baseline, assignment of abnormalities) and statistic will be based on the mean value of the triplicates/duplicates.

The values of the original members of a triplicate/duplicate will be listed.

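### The QTcF stopping rule is stated in two forms, cannot be met from scheduled ECGs alone, and relies on a value whose source the documents describe inconsistently

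*Protocol*

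**What the plan says.** **The rule.** Protocol 4.3.5 lists QTcF of 501 ms or more, or a rise of more than 60 ms from Visit 2, as a reason to discontinue study drug when seen "on at least 2 separate ECGs at the same visit".

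**Its restatement.** Protocol 6.5.4 repeats both thresholds and says that subjects with QTcF at that level or "an increase from baseline >60 ms should be discontinued from IMP (see Section 4.3.5"; the cross-reference is part of the sentence. The two-ECG condition is not repeated.

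**The recordings.** Protocol 6.5.4: "Triplicate ECGs will be performed at baseline (Visit 2) only within a time span of 6 minutes". Section 6.1.1 specifies "12-lead ECG (Visit 3 and 6, single" and "12-lead ECG (Visit 8, single", and also marks Visit 9/EOT and Visit 10/EOS as single.

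**The source of QTcF.** Protocol 6.5.4 lists uncorrected QT among the parameters to record and adds that "QTcF will be derived during the statistical analysis". SAP 5.3.3.2 states: "The QTcF values will be used as available in the database".

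**The concern.** A stopping rule should give one answer for one set of recordings, and the schedule should supply the recordings it needs. Here a single on-treatment ECG over a threshold meets the wording of Section 6.5.4 but not that of Section 4.3.5. The second ECG that would settle the matter is neither scheduled nor triggered by any instruction. The quantity being judged is also said to be derived at the analysis stage, although investigators must act on it while subjects are on treatment.

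This is a safety matter. Protocol 2.4 and 4.3.4.2 allow QT-prolonging medication case by case, and Section 2.4 provides ECG monitoring with central reading for the duration of the study. Sites that rely on different sections could handle the same tracing differently.

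**Working it through.** The plan gives no figure to reproduce on this point. The check is a count of scheduled recordings followed by a comparison of passages.

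**Step 1. Scheduled ECGs per visit against the two that Section 4.3.5 needs** (Protocol 6.1.1, 6.5.4, 6.10).

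| Visit | Scheduled ECGs | Two available? |
|---|---|---|
| 2 (baseline) | 3 | Yes, but this is the reference for the rise |
| 3, Week 2 | 1 | No |
| 6, Week 12 | 1 | No |
| 8, Week 20 | 1 | No |
| 9, Week 26 / EOT | 1 | No |
| 10 / EOS | 1 | No (off drug) |

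On-treatment visits that supply two ECGs: 0 of 4 (Visits 3, 6, 8, 9). Visit 9 ends treatment, so a rule for stopping drug has little left to act on there. For Visits 3, 6 and 8 the count is 0 of 3. An extra ECG is needed every time.

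**Step 2. Is the extra ECG instructed?** Sections 6.1 and 6.2 say that safety assessments should be repeated at other time points, and others added, if clinically indicated. Section 6.5 allows additional assessments. These passages permit a repeat ECG but do not tie one to a threshold crossing or to the same visit. The liver criteria in Section 4.3.5 are more explicit: three of the four say to withhold, repeat the tests and discontinue if confirmed. The confirmation procedure that follows them has the subject return to the site, preferably within 48 hours, for a work-up built on laboratory tests. A return is a different visit and would not supply a second ECG at the first one.

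**Step 3. One single ECG over a threshold, under each section.**

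- Section 4.3.5: condition not met, because one ECG is fewer than two.
- Section 6.5.4 read alone: discontinue.
- Section 6.5.4 with its cross-reference followed: the reader reaches Section 4.3.5 and needs a second ECG that no passage tells the site to record.

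**Step 4. When QTcF is needed and where it comes from.**

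| Place | Use or source | Timing |
|---|---|---|
| Protocol 4.3.3, exclusion 5.1 | Eligibility limits of 450 ms (male) and 460 ms (female) | Before randomization |
| Protocol 4.3.4.2 | Interrupting study drug when a QT-prolonging drug is indicated, considering baseline QTcF and its change | During treatment |
| Protocol 4.3.5 | Stopping study drug | At the visit |
| Protocol 6.5.4 | Derived in the statistical analysis | After the data are collected |
| SAP 5.3.3.2 | Taken from the database | Already present at analysis |

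Three in-study uses do not fit the timing in Section 6.5.4, and the SAP names a different source.

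**Step 5. Can a site obtain QTcF at the visit?** The protocol's definition of terms gives QTcF = QT × (1000/RR)^(1/3). With assumed values of QT 460 ms and RR 770 ms (not from the documents), QTcF = 460 × (1000/770)^(1/3) = 501.9 ms, just over the 501 ms threshold. One ECG is therefore enough to compute it. However, the formula calls for a directly measured RR, which is not in Section 6.5.4's list of recorded parameters. No passage tells the site to make the calculation at the visit.

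**Step 6. Timing of the central report.** Section 6.5.4 requires immediate investigator review of the tracing, then assessment of flagged abnormalities once the central report is received. A report that arrives after the subject has left cannot prompt a second ECG at that visit.

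**The case against.** The strongest reply is that the schedule sets a minimum. Extra safety assessments are expressly allowed, the investigator reviews each ECG while the subject is present, and a second tracing can then be recorded. Section 6.5.4 is an abbreviated restatement that points to the full rule, so a site acts on the short form only if it ignores the reference. Section 4.3.5 separately lets the investigator consider stopping treatment over concerns about the subject's safety, so a site without two ECGs is not prevented from acting.

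All of this is correct, and it limits the point. A reader might infer that the stopping rule cannot be applied at all. The documents do not support that, because an unscheduled repeat satisfies Section 4.3.5. A reader might also infer that QTcF does not exist until the analysis. The documents do not say so: exclusion 5.1 requires it before randomization, Section 4.3.4.2 has the investigator follow it over time, the formula is in the protocol, and the SAP expects it in the database.

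The reply does not close the gap. Permission to repeat is not an instruction to repeat, and a cross-reference does not make two different statements agree. The derivation remark in Section 6.5.4 still conflicts with the stopping rule and with the SAP.

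**Conclusion.** The point stands as an inconsistency that should be corrected. The QTcF rule appears with and without a two-ECG condition. None of the four on-treatment ECG visits supplies two scheduled recordings. No passage triggers the second recording, and the source and timing of QTcF differ between Protocol 6.5.4, the in-study uses and SAP 5.3.3.2.

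The count rests on Section 6.1.1's specification of single recordings and on Section 6.5.4's limiting triplicates to baseline. How often the discrepancy would matter cannot be estimated, because the documents give no expected rate of threshold crossings and do not say how quickly central reports return.

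A reader might go further and infer a loss of Week 26 FVC data through inconsistent stopping. Without a rate, the documents do not support a claim of any such effect on the primary analysis. The case for correction rests on the clarity of a safety rule.

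**What to change.** Reconcile Protocol 4.3.5, 6.1.1, 6.5.4 and the schedule of activities with SAP 5.3.3.2 so that:

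1. one QTcF trigger is stated in the same words wherever it appears;
2. the ECGs on which that trigger depends are obtained at the visit where it is assessed, with an explicit site instruction if this needs a recording beyond the scheduled one;
3. one named QTcF source, available during the study, serves eligibility, drug interruption, stopping and the SAP analysis, and the derivation remark in Section 6.5.4 is brought into line with it.

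Which trigger applies is a clinical decision for the sponsor's medical team and is not proposed here. The cost is protocol and SAP wording, a site instruction, and at most an occasional repeat ECG.
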